1. To demonstrate that vaccination with QIVc elicits an immune response that is not inferior to that of a US-licensed QIV, in subjects 6 months through 47 months of age, as measured by hemagglutination inhibition (HAI) assay for A/H1N1, B/Yamagata and B/Victoria strains and by microneutralization (MN) assay for A/H3N2 strain, using cell-derived target viruses

Secondary Immunogenicity Objectives:

1. To describe the immunogenicity of QIVc and US-licensed QIV by HAI assay for A/H1N1, B/Victoria, and B/Yamagata strains, and by MN assay for A/H3N2 strain, using egg-derived target viruses
2. To describe the immunogenicity of QIVc and US-licensed QIV by HAI assay for A/H1N1, B/Victoria, and B/Yamagata strains and by MN assay for A/H3N2 strain, using cell-derived target viruses
3. To describe the immunogenicity of QIVc and US-licensed QIV by MN assay for A/H1N1, B/Victoria, and B/Yamagata strains, in a subset of subjects

Secondary Safety Objective:

1. To evaluate the safety and reactogenicity of QIVc and US-licensed QIV

Exploratory Immunogenicity Objectives:

1. To evaluate the homologous cell-mediated immunity (CMI) response, prevaccination and postvaccination, in a small population of subjects
2. To further describe the immune response to vaccination, additional immunogenicity analyses may be conducted such as HAI assay for A/H3N2 using cell- and egg-derived target virus

Name of Sponsor:	Protocol number:	Generic name of study vaccine(s):
Seqirus	V130_10	Cell-Based Quadrivalent Subunit Influenza Virus Vaccine (QIVc) US-licensed Egg-Based Quadrivalent Influenza Vaccine (QIV)

Study Design:

This phase 3 clinical study is a randomized, observer-blind, comparator controlled, multicenter study of QIVc versus a US-licensed QIV in children 6 months through 47 months of age. The study features a 2:1 randomization between QIVc and US-licensed QIV. Based on influenza vaccination history, subjects will receive either 1 or 2 doses of either QIVc or US-licensed QIV comparator (see [Table 1-1](#) for previously vaccinated subjects and [Table 1-2](#) for not previously vaccinated subjects). The study will be conducted in approximately 2502 healthy subjects: 2418 subjects for evaluation of immunogenicity and 84 subjects for evaluation of CMI response.

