Both QIVc and the US-licensed QIV will be administered intramuscularly (IM), in the anterolateral aspect of the thigh or into the deltoid muscle. For both QIVc and US-licensed QIV, either 1 or 2 doses will be administered depending on each subject's influenza vaccination history. If 2 vaccinations are given, the administration interval will be approximately 28 days.		
Study vaccine:		
A dose of 0.5 mL of QIVc (Flucelvax Quadrivalent) contains purified 15 µg viral envelope-glycoprotein hemagglutinin (HA) of each of the four (4) influenza strains recommended by WHO for inclusion in the quadrivalent vaccine formulation for the influenza season corresponding to the season of conduct of study.		
Comparator vaccine:		
Afluria Quadrivalent will be administered as the US-licensed QIV comparator, following dose recommendations described in the US Package Insert (USPI).		
Subjects 6 months through 35 months of age will receive 0.25 mL (1 or 2 doses, depending on influenza vaccination history), while subjects 36 months through 47 months of age will receive 0.5 mL (1 or 2 doses, depending on influenza vaccination history).		
Immunogenicity Endpoint		
Immunogenicity of study vaccines will be evaluated at Day 1 and Day 29 for "previously vaccinated" subjects or Day 1 and Day 57 for "not previously vaccinated" subjects.		

Primary Immunogenicity Endpoints

Serum HAI antibody titer against A/H1N1, B/Victoria and B/Yamagata vaccine strains at Day 29/57, using cell-derived target virus:

- Geometric Mean Titer (GMT) by HAI assay
- Seroconversion rate (SCR) defined as the percentage of subjects with either a prevaccination HAI titer $<1:10$ and a postvaccination HAI titer $\geq 1:40$, or a prevaccination HAI titer $\geq 1:10$ and a ≥ 4 -fold increase in postvaccination HAI titer

Serum neutralizing antibody titer against A/H3N2 vaccine strain at Day 29/57, using cell-derived target virus:

- GMT by MN assay
- SCR defined as the percentage of subjects with either a prevaccination MN titer $<1:10$ (Lower Limit Of Quantification [LLOQ]) and a postvaccination MN titer $\geq 1:40$ ($4 \times \text{LLOQ}$), or a prevaccination MN titer $\geq 1:10$ (LLOQ) and a ≥ 4 -fold increase in postvaccination MN titer

Derived Variables:

- The GMT ratio (QIV/QIVc) for each strain
- The inter-group difference in the SCRs (QIV minus QIVc) for each strain

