The noninferiority of QIVc compared to the US-licensed QIV will be assessed by HAI GMT and HAI Seroconversion rates against cell-derived target viruses for A/H1N1, B/Victoria and B/Yamagata strains and by MN GMT and MN seroconversion rates against cell-derived target virus for H3N2 strain. All eight primary hypotheses need to be met in order to demonstrate noninferiority.

Specifically, QIVc will be considered to be noninferior to the US-licensed QIV if, for each of the four strains, the following statistical criteria are met:

A/H1N1 and B strains:

- The upper bound of the two-sided 95% confidence interval (CI) on the ratio of the HAI GMTs does not exceed 1.5. The HAI GMT ratio will be calculated as HAI GMT US-licensed comparator QIV *divided* by HAI GMT QIVc.
- The upper bound of the two-sided 95% CI on the difference between the HAI SCR does not exceed 10%. The HAI SCR difference will be calculated as HAI Seroconversion US-licensed comparator QIV *minus* HAI Seroconversion QIVc. The 95% CI will be computed based on the binomial distribution.

A/H3N2 strain only:

- The upper bound of the two-sided 95% CI on the ratio of the MN GMT does not exceed 1.5. The MN GMT ratio will be calculated as MN GMT US-licensed comparator QIV *divided* by MN GMT QIVc.
- The upper bound of the two-sided 95% CI on the difference between the MN SCRs does not exceed 10%. The MN SCR difference will be calculated as MN Seroconversion US-licensed comparator QIV *minus* MN Seroconversion QIVc. The 95% CI will be computed based on the binomial distribution.

To determine the GMT ratio, a general linear model (GLM) will be fitted on log-transformed postvaccination HAI (or MN) titers and terms for covariates (with further details specified in the protocol and Statistical Analysis Plan [SAP]).

From the model an adjusted difference in least-square means (on the log scale) will be produced with 95% confidence limits. The estimated difference and the confidence limits will be back-transformed to obtain an adjusted GMT ratio with 95% confidence limits. Each of the 4 strains will be analysed separately. The adjusted GMT ratio will be the result for which the noninferiority assessment will be based on.

Secondary Immunogenicity Analysis:

Secondary immunogenicity analyses of GMT, GMRs, seropositivity rates, percentages of subjects with HAI titer $\geq 1:40$, SCRs, GMT ratios, and SCR differences will be carried out in a similar fashion as in the primary immunogenicity analyses.

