8.5 Sample Size and Power Considerations

QIVc will be tested against comparator, i.e. US-licensed comparator QIV. The treatment randomization ratio is 2:1 (Seqirus QIVc: Comparator QIV). This study is designed to achieve at least 90% power to demonstrate noninferiority for all of the 8 endpoints: seroconversion rates for 4 strains and GMT for 4 strains using a one-sided alpha of 0.025 for each comparison. No alpha adjustment for multiple endpoints will be made.

For comparisons of SCR a noninferiority margin of 10% (Comparator QIV-Seqirus QIVc) will be employed. It is assumed that the SCRs for A/H1N1, B strains and A/H3N2 based on TIVc are 81%, 69% and 85% respectively. These estimates are based on the estimated SCR rates of historical data, namely from study V58P16.

It is also assumed that the expected difference between antibody titers (QIV minus QIVc) is consistent with the SCR differences reported as per V58P16, namely 7% for A/H1N1 and 5% for A/H3N2 (based on the MN assay).

It is assumed there is no difference between Seqirus QIVc and the comparator QIV for the B/strain.

For comparison of GMT ratio a noninferiority margin of 1.5 (Comparator QIV/ Seqirus QIVc, equivalent to a difference on the log scale of 0.405465108) will be employed for the assessment of the A/H1N1, A/H3N2 and B strains. It is assumed that the GMT ratio's for A/H1N1, A/H3N2 and B strains for QIVc are 1.49 for the A/H1N1, 1.00 for the A/H3N2 (based on the MN Assay) and 0.84 for the B-strain. These GMT ratio estimates are consistent to those observed from protocol V58P16. It is assumed that the standard deviation of log (titer) is 1.3 across all strains.

Under these assumptions and with n evaluable = 1450 in the Seqirus QIVc group and 725 in the Comparator QIV the power for 4 GMT ratio endpoints is 94.90% and the power for 4 SCR endpoints is 99.40%. The overall global power of the 8 endpoints is then $94.90\% * 99.40\% = 94.33\%$. This provides a total N evaluable = 2175. Allowing for a 10% drop-out, 2418 subjects will be recruited for immunogenicity assessment. Approximately 84 additional subjects between 24 through 47 months of age will be enrolled to study CMI response, in order to have approximately 50 and 25 evaluable subjects in the QIVc

and Comparator QIV groups, respectively. Thus, approximately 2502 subjects will be enrolled in this study.

Sample size calculations were performed using PASS v12.0.02.

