Table 8.5-1 summarizes the list of all co-primary endpoints with strains, the planned noninferiority margin and underlying assumptions used for the sample size computations.

Table 8.5-1 Summary of Assumptions Used for Sample Size Calculations

NI comparison	A/H1N1	A/H3N2	B strains
Test significance level, alpha (1-sided)	2.50%	2.50%	2.50%
Noninferiority Margin for the SCR comparison (%)	10	10	10
Assumed true SCR	81%	85%	69%
Power for SCR comparison tests for each strain (%)	100%	100%	99.7%
Global Power for 4 SCR Endpoints	99.40%		
Noninferiority Margin for the GMT ratio	1.5	1.5	1.5
Common Standard Deviation of \log_e (titer)	1.3	1.3	1.3
Power for GMT ratio tests for each strain (%)	100%	100%	97.42%
Global Power for 4 GMT ratio Endpoints	94.90%		
Global Power for 8 Co-primary Endpoints	94.33%		

Abbreviations: GMT = geometric mean titer; NI = noninferiority; SCR = serconversion rate.

Sample size calculations were performed using PASS v12.0.02.

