6.5.1.3 Statistical Methods

All statistical analyses for HAI (or MN) titers will be performed on the logarithmically transformed (base 10) values. Individual HAI titers below the detection limit (<10) will be set to half of that limit (5). Individual MN titers below the LLOQ, will be set to half of that limit ($1/2 * \text{LLOQ}$).

Co-primary immunogenicity endpoints of GMT and SCR for each virus strain contained in the vaccine will be assessed in subjects 6 Months through 47 Months of Age overall.

Statistical Analysis Plan

Sponsor Name: Seqirus
Sponsor Protocol ID: V130_10

Primary analysis will be performed in subjects 6 Months through 47 Months of Age for the Per-Protocol Set. The difference in SCRs will be presented with exact 95% CIs. Each of the four strains will be analyzed separately.

For immunogenicity data, the immunogenicity analysis will comprise a complete case analysis only, without introducing any bias. Imputation methods will not be used.

To determine the GMT ratio (adjusted analysis) a general linear model (GLM) will be fitted on log transformed (base ten) post-vaccination HAI (or MN) titer as the outcome variable and terms for covariates: vaccine treatment, pre-vaccination HAI (or MN) titer, age stratum, gender, vaccination history, age-by-vaccine interaction and study site. Potential covariate interaction effects will also be examined in the fit of the GLM. From the model, an adjusted difference in least square means (on the log scale) will be produced with 95% confidence limits. The estimated difference and the confidence limits will be back transformed to obtain an *adjusted GMT ratio* with 95% confidence limits. Each of the four strains will be analyzed separately. The adjusted GMT ratio will be the result for which the non-inferiority assessment of the HAI (or MN) GMT co-primary endpoint will be based on.

The statistical models might be reduced in case they fail to converge.

The complete set of covariates that will be used in the model to calculate the adjusted GMT ratio will include treatment group (2 treatments), pre-vaccination GMT titer (value), age strata (2 categories, 6 through 23 months or 24 through 47 months), gender (male or female), influenza vaccination received prior year (Yes or No), and investigator site (site identifier).

The GLM specification is:

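### The four deciding GMT limits appear to rest on one residual variance for both vaccines under 2:1 allocation, so the per-test error departs from 2.5% if titer spread differs, and exceeds it only if the smaller QIV arm is the more variable.

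*Protocol*

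**What the plan says.** The protocol synopsis allocates unequally: "The study features a 2:1 randomization between QIVc and US-licensed QIV". Its criterion for A/H1N1 and the B strains is: "The upper bound of the two-sided 95% confidence interval (CI) on the ratio of the HAI GMTs does not exceed 1.5". The same bound applies to the A/H3N2 microneutralization GMTs. Protocol 8.5 sets each test "using a one-sided alpha of 0.025 for each comparison", and success requires all eight endpoints (Protocol 8.2, SAP 6.5.1.1).

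The synopsis gives the source of the limits: "To determine the GMT ratio, a general linear model (GLM) will be fitted on log-transformed postvaccination HAI (or MN) titers and terms for covariates". The model is fitted to log10 titers with vaccine, age stratum, gender, vaccination history, prevaccination titer, site and, if significant, age stratum by vaccine (Protocol 8.4.2.3.3, SAP 6.5.1.3). From it, "an adjusted difference in least square means (on the log scale) will be produced with 95% confidence limits", which is then back-transformed.

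Planning also uses one spread. Protocol Table 8.5-1 has a row labelled "Common Standard Deviation of" log titer, with 1.3 for every strain. No SD by vaccine group is given.

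The visible text names no group-specific variance, robust standard error, unequal-variance degrees of freedom or check of equal spread. Nor does it use the words pooled or equal variance for this model. The model code in SAP Appendix B is blacked out.

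**The concern.** With equal arms, a single residual variance does no harm to a difference in means in large samples, because the pooled and true standard errors coincide. With 2:1 allocation they do not. The pooled variance takes two thirds of its weight from QIVc. Under equal spread, two thirds of the sampling variance of the difference comes from QIV. If QIV titers are the more variable, the interval is too narrow and noninferiority is declared too easily. If they are less variable, it is too wide and power is lost.

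Two features of the plan bear on whether spread is equal:

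- **Flooring.** HAI titers below 10 are set to 5, and MN titers below the LLOQ to half of it. At the noninferiority margin QIV titers are 1.5 times higher, so the QIVc arm is floored more and its spread is compressed more. That is the anti-conservative direction.
- **Comparator volume.** The comparator volume changes at 36 months, while the model's age strata split at 24 months. Any volume effect within the older stratum would enter the QIV residuals only.

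No visible planned analysis would show the problem. The sensitivity work in SAP Appendix C concerns missing data.

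**Working it through.** **Inputs from Protocol 8.5 and Table 8.5-1.** 1450 QIVc and 725 QIV evaluable; SD of ln(titer) 1.3; margin 1.5 ("equivalent to a difference on the log scale of 0.405465108"); one-sided 0.025; assumed B-strain ratio QIVc/QIV 0.84.

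**Reproducing the plan's figure.** SE = 1.3 × √(1/1450 + 1/725) = 0.0591. B-strain power = Φ[(0.4055 − ln(1/0.84))/0.0591 − 1.96] = Φ[(0.4055 − 0.1744)/0.0591 − 1.96] = 97.43%. With the noncentral t it is 97.42%, as stated. The A-strain powers are about 100%, so the four GMT tests give 0.9742² = 94.9%, also as stated.

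**Error of the single-variance interval.** Let r be the residual SD ratio QIV/QIVc (an assumption), with QIVc SD s.

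- Pooled variance = s²(1450 + 725r²)/2175 = s²(2 + r²)/3.
- Pooled SE² = s²(2 + r²)/1450.
- True SE² = s²/1450 + r²s²/725 = s²(1 + 2r²)/1450.
- Pooled SE / true SE = √[(2 + r²)/(1 + 2r²)].
- One-sided error at the margin = Φ(−1.96 × that ratio).

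For r = 1.2: √(3.44/3.88) = 0.9416, and Φ(−1.8455) = 3.25%. The error depends only on r and the allocation, so it also applies to residual SDs after covariate adjustment.

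The last column is B-strain power with separate variances, holding the pooled SD at 1.3.

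| r (QIV/QIVc) | pooled SE / true SE | one-sided error | B-strain power, separate variances |
|---|---|---|---|
| 0.8 | 1.076 | 1.75% | 98.8% |
| 0.9 | 1.036 | 2.1% | 98.2% |
| 1.0 | 1.000 | 2.5% | 97.4% |
| 1.1 | 0.969 | 2.9% | 96.6% |
| 1.2 | 0.942 | 3.25% | 95.7% |
| 1.5 | 0.879 | 4.25% | 93.0% |

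At 1:1 allocation the two standard errors are equal and the error stays at 2.5% for every r.

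**Simulation check.** 20,000 trials per scenario, two groups, no covariates. At r = 0.8, 1.0, 1.25 and 1.5 the single-variance interval gave 1.6%, 2.6%, 3.4% and 4.2%. Separate variances gave 2.3%, 2.6%, 2.5% and 2.4%.

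**How large might r be?**

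- *Comparator volumes.* Assume ages spread evenly over 6 to 47 months, so 12/42 = 0.286 of the QIV arm receives the larger volume. A k-fold titer difference between volumes adds 0.286 × 0.714 × (ln k)² to the QIV variance, ignoring what the age term absorbs. For k = 1.5 this is 0.034, so r = √(1 + 0.034/1.69) = 1.01. For k = 2 it is 0.098, so r = 1.03. The errors are 2.54% and 2.61%.
- *Flooring at 5.* Assume lognormal titers with SD 1.3 in both arms before flooring, and floored GMTs in the ratio 1.5. At QIVc GMTs of 10, 16, 21 and 40, r is 1.18, 1.08, 1.05 and 1.01, and the errors are 3.2%, 2.8%, 2.7% and 2.6%. The documents give no absolute GMTs, so this is a range. It fades at high titers.

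**The case against.** The strongest case against has five parts.

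1. **The harmful condition is not shown.** No SD by arm is given, and the ratios of 1.1 and above are assumptions. This stands. The comparator volumes alone leave the error at essentially its nominal value, and flooring matters only at low GMTs.
2. **One variance is inferred.** The code is redacted and could hold a variance option. This also stands. A single residual variance is still the natural reading of an ordinary general linear model, and the text that defines the deciding analysis should not leave the point to hidden code.
3. **Few decisions would change.** With SD 1.3 the upper limit is the estimate times 1.123 with one variance and times 1.131 with separate variances at r = 1.2. The decision differs only for estimates between 1.5/1.131 = 1.326 and 1.5/1.123 = 1.336. At the planned B-strain ratio the chance of that is about 0.9% per strain. This is correct at the planned ratios, but the stated error rate is defined at the margin.
4. **All eight tests must pass.** False overall success therefore cannot exceed the error of any one truly inferior endpoint. This is correct, but the bound can be approached when a single strain is inferior and the others pass easily.
5. **The simulation had no site effects or other covariates.** This is a fair limit on the check.

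A reader might also see an inconsistency in SAP 6.5, where the within-group GMT limits use each group's own standard error. That does not follow. A one-group interval must use that group's spread, and this says nothing about the contrast. Different expected mean responses by strain do not help either, since each strain is analyzed separately. Different cell and egg strain names suggest at most a shift in means.

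**Conclusion.** The concern holds in a limited, conditional form. As described in the visible text, the four GMT intervals keep their 2.5% one-sided error only if residual spread is equal in the two vaccine groups. The 2:1 allocation is what makes this matter. The departure has a direction: above 2.5% if QIV is the more variable, below it if QIV is the less variable.

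A reader might infer that the error rate fails whenever spread differs, or that the trial's overall error is inflated to the per-strain figures. The documents support neither. In one direction the test is conservative, and the per-strain rates are upper bounds at study level.

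The likely size is modest: about 2.5% to 2.6% from the comparator volumes alone, and about 2.6% to 3.2% from flooring for assumed QIVc GMTs from about 40 down to 10. Larger figures need SD ratios that the documents do not support. The change is still worth making, because it corrects the interval in both directions at almost no cost.

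**What to change.** In SAP 6.5.1.3 and Protocol 8.4.2.3.3, before unblinding for the treatment-period analysis:

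- Keep the model terms. State that the 95% limits of the adjusted GMT ratio that are compared with 1.5 come from a fit with a separate residual variance for each vaccine group and Satterthwaite degrees of freedom. Name this one method and leave no alternatives open.
- Use unequal-variance (Welch) limits for the unadjusted GMT ratio.
- Report the residual SD by vaccine group for each strain.

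The cost is a sentence in each document and one model option; no extra data are needed. If spreads are equal, the limits are practically unchanged and B-strain power stays at 97.4%. If QIV is more variable, the interval is slightly wider, with B-strain power 96.6% at a ratio of 1.1 and 95.7% at 1.2. If QIV is less variable, power rises, to 98.8% at a ratio of 0.8.

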1. BACKGROUND AND RATIONALE

1.1 Background

Influenza is an infectious disease caused by the influenza virus, an orthomyxovirus with two clinically relevant types (Type A and B). The disease is characterized by the abrupt onset of respiratory and systemic symptoms, such as fever, cough, sore throat and rhinitis. It occurs in epidemics throughout the northern and southern hemisphere winter months in temperate climates. Influenza Type A/H1N1, A/H3N2, and Type B/Victoria and B/Yamagata strains have circulated and caused disease in humans on a global basis since 1977 (Fiore et al. 2010), with a high susceptibility to severe influenza in children (Izurieta et al. 2000; Bourgeois et al. 2006). Children <5 years, and particularly those <2 years of age, are at high risk of infection and are a priority for annual seasonal influenza vaccination throughout the world (World Health Organization [WHO] 2012; American Academy of Pediatrics Committee on Infectious Diseases 2016). With vaccination as the recommended method to prevent influenza, both childhood influenza disease burden and community viral transmission could be reduced (Mertz et al. 2016).

One of the challenges of protecting children against influenza is providing a vaccine with an antigenic match against the circulating strains in a given influenza season. Since 1983, two evolutionarily distinct lineages of influenza B viruses have co-circulated in the human population globally (Rota 1990) and influenza B viruses account for roughly 20% of total influenza events in all regions of the world (Ciani et al. 2015). As only one B lineage is selected for inclusion in current trivalent influenza vaccines (TIVs) and there has been no demonstrated cross protection between the two lineages (Peltola et al. 2003; Hu et al. 2004), there is the risk of a mismatch for the influenza B strain (Couch, 2007; Belshe, 2010; Orsi et al. 2018). Since patients infected with influenza B are usually younger than patients infected with influenza A, the effectiveness of vaccination in children seems more dependent on adequate matching (Jayasundara et al. 2014; Ciani et al. 2015; Orsi et al. 2018). To address this, quadrivalent influenza vaccines (QIV) were developed containing B strains from both lineages.

Seqirus' Flucelvax Quadrivalent, is a cell based quadrivalent inactivated subunit influenza vaccine (QIVc) prepared from virus propagated in Madin Darby Canine Kidney (MDCK) cells, and approved by the Food and Drug Administration (FDA) for use in children 4 years and older. QIVc has a formulation with 2 influenza A strains and 2 influenza B strains updated annually as recommended by the WHO for a specific influenza season, and addresses the unmet medical need of better vaccine antigenic matching against co-circulating influenza B strains. A shift from egg- to cell-culture based manufacturing platforms has several advantages, allowing for the possibility to work directly with wild-type viruses, avoiding the generation of egg-adaptive mutations in the HA protein, increasing surge capacity in the event of a pandemic, and providing better manufacturing

control through a closed-system fermentation process ([Lambert and Fauci 2010](#)). In addition, cell culture-derived influenza vaccines do not require extensive advanced planning and can, in principle, be vital for responding to the threat of an emerging pandemic.

A marketing authorization for TIVc (Flucelvax) was received from the FDA in the United States (US) in November 2012, for use in subjects of 18 years of age and older. A supplemental Biologics License Application (sBLA) to extend the age indication of TIVc to 4 years and above was submitted to the FDA in November 2014. This was followed, in April 2015, by a Biologics License Application (BLA) submission to obtain marketing authorization of QIVc for the prevention of seasonal influenza in both adult and pediatric subjects (≥ 4 years of age). In May 2016, QIVc was approved by the FDA for use in people 4 years of age and older.

The goal of the current observer-blind, comparator controlled study in children 6 months through 47 months of age is to demonstrate that vaccination with QIVc elicits an immune response that is not inferior to that of a US-licensed QIV containing the recommended strains for the season. Immunogenicity will be evaluated at Day 1 and Day 29 (previously vaccinated subjects) or Day 1 and Day 57 (not previously vaccinated subjects). For noninferiority assessment, the immunogenicity will be evaluated through measurement of serum HAI antibody titers for all influenza strains, except for A/H3N2. Recent evolutionary changes in A/H3N2 hemagglutinin have resulted in the loss of capacity to agglutinate, and therefore the two A/H3N2 endpoints will be assessed using the MN assay.

